### Study Setting and Participants:

Children aged 2 to 20 years with a known history of asthma who presented to the Emergency Department at Women and Children's Hospital of Buffalo/Oishei Children's Hospital between April 2015 and March 2018 with an acute exacerbation of mild or moderate asthma were eligible for the study. Asthma severity was defined by Pediatric Asthma Scores[2, 12] (PAS). Mild asthma is defined as: PAS of 5 to 7; Moderate asthma is defined as: PAS of 8 to 11; Severe asthma is defined as: PAS of 12 or more. History of asthma is defined by physician diagnosis of at least one prior episode of wheezing which responded to beta agonists. Patients were excluded from the study if they had signs of severe asthma exacerbation (PAS of 12 or more), had used oral steroids in the last 2 weeks, had chronic lung disease (e.g., cystic fibrosis), had been given parenteral steroids, or if they vomited two doses of oral steroids in emergency department.

Research assistants screened asthma patients through the electronic medical record between the hours of 8 a.m. and 11 p.m. 7 days a week. Patients were approached sequentially based on registration time. If a patient appeared to meet study criteria, his/her ED treating physician was approached by the research assistant for identifying patient's eligibility. If a patient was fully eligible, the legal guardian and/or patient were approached for consent.

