#### Analytic Plan:

Descriptive characteristics were computed for all patients combined and separately by dexamethasone group assignment. Categorical variables were reported as proportions in percentage, and continuous level variables as means and standard deviations. Separate independent t-tests were used to assess differences by group for post-discharge outcomes of interest including days for symptoms to resolve. Separate binary logistic regression adjusting for age, gender and severity of exacerbation were conducted to assess group differences in post-discharge outcomes including patients who had a return visit for unresolved asthma symptoms (ED, primary care or urgent care), days to symptom resolution, any missed school days between discharge and follow-up, rates of vomiting, and side-effects (changes in appetite, insomnia, mood swings); odds ratios with 95% confidence intervals were reported. Similar analyses were conducted to compare events and side effects between Groups 1 and 2 by asthma severity, using an intention-to-treat approach. Based on our clinical experience, we based our a-priori sample size calculation on an estimated non-inferiority limit of 11% and a rate of 12% return for asthma for each group. With a power of 80% and alpha of 0.05, a minimum sample size of 216 (108 subjects per group) was determined. All statistical tests were two-tailed, and analyses conducted with SYSTAT 13 (SYSTAT Software, 2004).

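### The 108 per group gives 80% power only at a one-sided 5% level, but the plan declares every test two-tailed; against a two-sided 95% interval for the risk difference, power is about 70%

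*Combined protocol and SAP*

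**What the plan says.** All the relevant text on sizing and testing is in the Analytic Plan. The sample size rests on "an estimated non-inferiority limit of 11% and a rate of 12% return for asthma for each group". The next sentence gives the result: "With a power of 80% and alpha of 0.05, a minimum sample size of 216 (108 subjects per group) was determined". It does not say whether that alpha is one-sided or two-sided.

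The section closes with "All statistical tests were two-tailed". For binary outcomes, return visits included, it plans logistic regressions adjusted for age, gender and severity, "conducted to assess group differences in post-discharge outcomes", and the output is described as "odds ratios with 95% confidence intervals were reported". No interval for a difference in return rates is specified, and no rule says how the 11% limit will be judged.

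Study Setting and Participants gives the enrolment period as "between April 2015 and March 2018".

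**The concern.** In a non-inferiority comparison only one tail matters. An alpha of 0.05 used one-sided puts 5% in that tail and corresponds to a 90% interval. Two-sided, it puts 2.5% there and corresponds to a 95% interval. The sample-size sentence leaves the choice open. The closing sentence of the section points to the second reading, whereas the number 108 comes from the first.

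The error rate behind a non-inferiority claim is therefore undefined, and the choice can reverse the conclusion. Take hypothetical counts of 16/108 returns after a single dose and 13/108 after two doses, a difference of 2.8 points with a standard error of 4.64 points:

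- 90% interval: upper limit 2.8 + 1.645 × 4.64 = 10.4 points, inside the limit.
- 95% interval: upper limit 2.8 + 1.960 × 4.64 = 11.9 points, outside it.

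The plan as written does not say which of these applies.

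**Working it through.** **Inputs, from the Analytic Plan.** Return rate 0.12 in each group (true difference 0), limit 0.11, power 0.80 (z = 0.842), alpha 0.05, and 108 per group. The 1:1 allocation is in Study Protocol. The scale of the limit is not stated; I read it as an absolute risk difference.

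**Reproducing the plan's figure.** With unpooled variance,

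n per group = (z_α + z_β)² × 2 × 0.12 × 0.88 / 0.11² = (z_α + z_β)² × 0.2112 / 0.0121.

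- One-sided 0.05 (z_α = 1.645): 107.9, so 108 per group and 216 in total. This matches the plan exactly.
- Two-sided 0.05, that is 0.025 in the relevant tail (z_α = 1.960): 137.0, so 137 per group and 274 in total.

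The other standard readings tried do not give 108 per group. A superiority test of 12% against 23% (pooled variance) needs 147 one-sided or 187 two-sided. For 12% against 1% the figures are 62 and 78. An equivalence test with two one-sided 0.05 tests needs about 150. Continuity correction of the superiority tests does not produce 108 either.

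**Power at 108 per group.** SE = √(0.2112 / 108) = 0.0442, and 0.11 / 0.0442 = 2.487.

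- 90% interval: Φ(2.487 − 1.645) = 0.800.
- 95% interval: Φ(2.487 − 1.960) = 0.701.

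**Sensitivity to the interval method.** Exact enumeration over two independent Binomial(108, 0.12) counts gives:

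| Method | 90% interval | 95% interval |
|---|---|---|
| Normal approximation | 80.0% | 70.1% |
| Wald | 80.7% | 70.9% |
| Newcombe | 79.3% | 67.8% |
| Farrington–Manning | 78.3% | 67.8% |

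**Sensitivity to the evaluable number.** The documents give no evaluable count. By the same formula, power with a 95% interval is 62% at 90 per group, 67% at 100 and 75% at 120.

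**Whether the planned odds ratio could serve instead.** At a 12% reference rate the 11-point limit corresponds to an odds ratio of (0.23/0.77) / (0.12/0.88) = 2.19, with natural log 0.784. The unadjusted SE of the log odds ratio is √(2 / (108 × 0.12 × 0.88)) = 0.419. Power is Φ(0.784/0.419 − 1.960) = 47% with a 95% interval (46% by enumeration) and 59% with a 90% interval (58% by enumeration).

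An illustration with 13/108 returns in both groups shows the difference in scale. The SE of the log odds ratio is √(2/13 + 2/95) = 0.418, so the 95% interval is 0.44 to 2.27, which crosses 2.19. On the risk-difference scale the 95% upper limit is 1.96 × √(2 × 0.1204 × 0.8796 / 108) = 8.7 points, inside 11. The same data fail on one scale and pass on the other.

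**The case against.** The strongest reply is that 108 is not miscalculated. It is right for a one-sided 5% non-inferiority test, a directional test suits a directional question, and the closing statement about two-tailed tests may have been meant only for the t-tests and regressions of group differences. The number 108 is also the only direct evidence of the level used in planning, and it points to one-sided 0.05. Further, the 70% belongs to an analysis the plan does not contain, 216 is described as a minimum, and enrolment is over. The odds-ratio figures rest on a converted limit, an unadjusted model and hypothetical counts.

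Much of this stands. The sample-size arithmetic is sound, the 70% is conditional on the interval named, and the odds-ratio figures only illustrate that scale matters.

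It does not rescue the plan. The closing statement covers all tests without exception, the only intervals specified are 95%, and nowhere is a one-sided 5% level declared. If that statement covers only the difference tests, then no planned analysis compares anything with the 11-point limit, and the 80% power attaches to no stated procedure. A non-significant two-tailed difference, or an odds ratio whose interval includes 1, would not establish non-inferiority.

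**Conclusion.** The concern holds. The stated 80% power is obtained only at a one-sided 5% level, which the plan does not declare and which its statement on two-tailed tests contradicts. Judged by a two-sided 95% interval for the risk difference, 108 per group gives about 70% power (68% to 71% across the methods checked). Restoring 80% at that level would have needed 29 more patients per group. Conversely, at the level that does yield 108, the one-sided error is 5%, twice the 2.5% that a two-tailed 0.05 implies.

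This rests on three assumptions: the 11% limit is an absolute difference, which is the reading that reproduces 108; the true return rate is 12% in both groups; and 108 per group are evaluable. It should be fixed. The sample size can stand, but the level and the decision rule must be stated before a non-inferiority conclusion can be interpreted.

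**What to change.** State in the Analytic Plan that non-inferiority on return visits is judged by comparing the upper confidence limit for the risk difference (single dose minus two dose) with 11 percentage points. Then take one of two routes.

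1. Keep a two-sided 95% interval, consistent with two-tailed testing, and restate the power of 216 patients as about 70%.
2. Only if one-sided 0.05 was the level set in advance, say so as an explicit exception to the two-tailed statement, use the 90% interval for the risk difference, and disclose the 5% one-sided error. Because enrolment ended in March 2018, this more lenient level should not be adopted once results are known.

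Under either route, keep the adjusted odds ratios as secondary description.

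The cost is two sentences and one risk-difference interval from data already collected, with no additional patients. The downside is a less favourable stated power under the first route, or an openly more lenient alpha under the second.
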